4.0 Study Design

4.1 Overview of Study Design

This experiment is a pilot study involving within and between group comparisons: AdSD compared to healthy controls, before and after rTMS delivery. Participants will be asked to come to the University of Minnesota for 1 session.

4.2 Anticipated Duration of the Clinical Investigation

The study's duration is anticipated to require 24 months from enrollment to the final report to the IRB.

If for any reason the study is terminated prior to the completion of subject participation, subjects would be withdrawn in accordance with Section 5.10.

4.3 Evaluation Criteria/Effectiveness

4.3.1 Primary Endpoint

The primary clinical endpoint will be corticospinal excitability measured with TMS testing before and after application of low-frequency rTMS.

4.3.2 Secondary Endpoints

Secondary endpoints will include clinical voice measures collected before and after rTMS procedures with a blinded assessment by a voice expert ([name], SLP, and [name], CCC-SLP, PhD) (Zraick *et al.*, 2011; Samargia *et al.*, 2016). In addition, self-reported voice disability will be assessed prior to rTMS delivery.

4.4 Study Population

4.4.1 Sample Size

This is the first pilot study of this kind and, therefore, no data are available for sample size calculation. Data from this pilot study will be used for effect size calculations for future investigations.

We plan to enroll 40 subjects (20 people with AdSD and 20 healthy controls). Due to the voluntary nature of our recruitment efforts, we expect a small number to dropout or fail screening qualifications. To ensure the needed number of enrollees, 50 subjects have been requested to be recruited in our IRB application.

Due to no direct benefit from participation, children will be excluded from this study.

4.4.2 Subject Recruitment

Healthy participants: Subjects will be recruited from the general public. University and local community advertisement will be made. Subjects will then self-identify if interested to learn more about the study.

Spasmodic dysphonia participants: Subjects will be recruited from several sources:

- 1. People with AdSD who have directly contacted [name] about research opportunities and patients that have participated in other studies from our team will be inquired if they are interested in this new pilot project. Study staff will contact only those who have given permission to be contacted about future studies.
- 2. [name] will ask his patient's that have AdSD if they are interested in hearing more about a study they may qualify for and if so will give him/her a flyer or direct him/her to talk to other study staff to learn more.
- 3. University and local community advertisement will be made. Postings also will be made on support group websites and organizations for dystonia. Subjects will then self-identify if interested to learn more about the study.

4.4.3 Subject Screening

Subjects will be screened by co-investigators using a list of exclusion criteria in person, by email or by phone. Screening questions include all inclusion and exclusion criteria. The maximum allowable time between screening and participation will be limited to the duration of the study. Prior to the start of the session, an on-site screening form will also be completed to ensure appropriate qualification. Females who could potentially be pregnant will be offered a pregnancy test at the CTSI and, if positive, they will not be allowed to participate. If they refuse testing as they are certain there is no risk they are pregnant, they will sign a waiver to clarify and be allowed to participate.

4.4.4 Prior and Concomitant Therapy

The risk of seizures is acknowledged but we emphasize that because of standards set for rTMS (Rossi et al., 2009; Rossini et al., 2015) this risk has been very well contained. Particularly due to our low rate stimulation and exclusion criteria we have minimized risk to participants. Our rTMS parameters are well within these safety guidelines (Rossi et al., 2009; Rossini et al., 2015). However, we still recognize that this remote risk requires a rigorous safety plan. We will ask subjects if they have any other medical conditions and if they are taking any medications. Important medication information such as any pro-epileptic medications and any history of seizure will be collected to screen those at risk for a TMS-induced seizure. Subjects will also be screened for previous surgeries that might include metal, indwelling medical devices, etc. In the event of a seizure during rTMS, subjects may be given oxygen by nasal cannula and, if the seizure does not abate in the expected time frame, the on-call physician may administer lorazepam or a related medication to interrupt the seizure. In the event of a headache from rTMS treatment, subjects may be given acetaminophen. See Brain Plasticity Lab white paper on TMS safety (attached).

Patients with AdSD who are currently receiving botulinum toxin injections will be asked about the duration between shots and scheduled to participate when their symptoms are reported to be the worst. This will typically be within 1 week of their regularly scheduled injections.

4.4.5 Inclusion Criteria

Subjects will be eligible to participate in the study if all of the following conditions exist:

Primary inclusion for spasmodic dysphonia:

- (1) 21-75 years of age
- (2) Diagnosis of adductor spasmodic dysphonia (AdSD)
- (3) Symptoms at worst severity if receiving regular botulinum injections

Primary inclusion for healthy participants (controls):

- (1) 21-75 years of age
- (2) Absence of vocal fold pathology

4.4.6 Exclusion Criteria

Subjects will be excluded from participation in the study if any of the following conditions exist:

Primary exclusion for participants with spasmodic dysphonia:

- (1) Other forms of dystonia
- (2) Vocal fold pathology or paralysis
- (3) Diagnosis of voice tremor
- (4) Laryngeal surgery
- (5) Laryngeal cancer or neurological condition other than dystonia
- (6) Contraindication to TMS*
- (7) Medications with effect on CNS
- (8) Inability to complete tasks associated with study
- (9) Adult lacking ability to consent

Primary exclusion for healthy participants (controls):

- (1) Any health condition or disability that would interfere with participation
- (2) Contraindications to TMS*
- (3) Medications with effect on CNS
- (4) Adult lacking ability to consent

*TMS contraindications:

- (1) The only absolute contraindication to TMS/rTMS is the presence of metallic hardware in close contact to the discharging coil (such as cochlear implants, deep brain stimulator, or medication pumps). In such instances there is a risk of inducing malfunctioning of the implanted devices.
- (2) Conditions classified as of increased or uncertain risk are listed below (Rossi et al., 2009; Rossini et al., 2015). Persons under those circumstances will be excluded from the study.
 - a. Pregnancy
 - b. Bipolar disorder
 - c. Epilepsy or history of seizure episodes in the past two years
 - d. Vascular, traumatic, tumoral, infectious, or metabolic lesion of the brain, even without history of seizure, and without anticonvulsant medication
 - e. Use of medications that potentially lower seizure threshold
 - f. Severe or recent heart disease
- (3) There is a small risk of fainting and hearing impairment with TMS/rTMS. For these reasons, the following precautions will be taken:
 - a. Fainting: To avoid fainting, we will ask subjects to eat a full meal and drink extra decaffeinated fluids before study visits. We will also apply TMS and rTMS in a reclining chair.
 - b. Hearing impairment: Participants will wear earplugs during the experiment to avoid hearing damage.

Additional information about risks and precautions for TMS/rTMS are included in the IRB protocol (Section 3).

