5.6 Study Protocol Compliance / Treatment Adherence

Subjects will be notified of the voluntary nature of participation. In the consent forms, subjects are made aware of the resources for those who wish to withdraw from the study. Criteria and procedures for withdrawing subjects are noncompliance and disqualification by previously outlined criteria, such as a developed neurological disease, implanted device, or pregnancy. See section 5.8 for more detail. Refer to section 5.8 for subject withdrawal and replacement.

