7.2.1 Anticipated Risks / Risk Mitigation

- 1. Personal information: There is a small risk of loss of confidentiality. Subjects will be asked if they have any medical conditions and if they are taking any medications. This is important to know so that only those subjects who meet the inclusion and exclusion criteria are accepted into the study. A number of procedures are in place to protect participant confidentiality. Every participant enrolled in the study will receive a unique code number. All records and results will be labeled with this code number and the code will be shared only with the study investigators. Any information that is included in published manuscripts (e.g. demographic information) will not be linked to any other information that would identify who the subject was.
- 2. TMS: Risks associated with TMS are rare but should be recognized and prevented with appropriate precautions. Serious adverse risks include the induction of a seizure. There have been reports of a seizure and induced mania from rTMS but none of these side effects have been reported with the type of rTMS that we are doing in this study. Mild adverse effects include fainting, headache, dental pain, and other changes in memory, mood, and hearing. The overall occurrence of a mild adverse event is 5% in sham and real TMS sessions combined (Maizey et al., 2013). Participants will be asked to complete the form "Subject Report of Symptoms" before TMS testing and at the end of the experiment so that the required actions are taken in case there are any changes to their health status. Participants will be instructed to contact study staff if they noticed any of the symptoms listed above after participation in the study. In addition, study staff may contact participants (via email or phone call) to follow-up on any issues or symptoms that occur during the experiment. People with a history of seizure within the last two years or a history of bipolar disorder will not be allowed to participate in this study. The tests may be discontinued without the participant's consent if the study team observes any abnormal responses. TMS delivery may also interfere with implanted devices and, thus, TMS is not appropriate for persons with medical devices such as deep brain stimulators, pace makers and medication pumps. Currently, the effects of TMS on hormonal cycles and the unborn fetus are unknown.

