7.3 Anticipated Adverse Events

Risks associated with TMS are rare but should be recognized and prevented with appropriate precautions. Serious adverse risks include the induction of a seizure. Mild adverse effects include fainting, headache, dental pain, and other changes in memory, mood, and hearing. TMS delivery may also interfere with implanted devices.

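### The TMS contraindication list in 4.4.6 is narrower than the protocol's own safety text on implanted devices: read literally, it does not exclude a volunteer with a pacemaker (minor, low probability)

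*Combined protocol and SAP*

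**What the plan says.** Eligibility is set in 4.4.6. Exclusion (6) for AdSD participants and exclusion (2) for controls both point, by an asterisk, to a TMS contraindication list in the same section.

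- Item (1) of that list: "The only absolute contraindication to TMS/rTMS is the presence of metallic hardware in close contact to the discharging coil". Its examples are cochlear implants, deep brain stimulators and medication pumps. The next sentence ties the device risk to that situation: "In such instances there is a risk of inducing malfunctioning of the implanted devices".
- Item (2) lists six excluding conditions, a to f. None is a device. The nearest is f: "Severe or recent heart disease".
- Controls, but not AdSD participants, also have a general exclusion: "Any health condition or disability that would interfere with participation".

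Other sections speak more widely about devices:

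- 7.2.1, item 2: "TMS is not appropriate for persons with medical devices such as deep brain stimulators, pace makers and medication pumps".
- 7.3: "TMS delivery may also interfere with implanted devices".
- 5.6, on withdrawal, refers to "disqualification by previously outlined criteria, such as a developed neurological disease, implanted device, or pregnancy".
- 4.4.4 says subjects are screened for metal from earlier surgery and for indwelling devices, but does not say what follows from a positive answer.

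**The concern.** The section that decides eligibility carries a proximity condition that the safety section does not. Pacemakers are named in 7.2.1 and are absent from 4.4.6.

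This matters because the protocol places the safeguard in the 4.4.6 list. Under 4.4.3 the screening questions cover the inclusion and exclusion criteria. Section 7.2 relies on screening against those criteria to keep participation safe. Item 3 of 4.4.7 removes a subject who comes to meet a listed exclusion. If the list is narrower than the safety statement it is meant to apply, two staff members working from different sections could reach different answers about the same volunteer. What is at stake is interference with an implanted device in a person whom the protocol itself regards as unsuitable for TMS.

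**Working it through.** No arithmetic applies. The check sets the texts side by side and follows one volunteer through them.

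**The two rules**

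| | 4.4.6, item (1) | 7.2.1, item 2 |
|---|---|---|
| What is covered | Metallic hardware | Medical devices |
| Condition on distance | Must be close to the coil | None |
| Devices named in both | Deep brain stimulator, medication pump | Deep brain stimulator, medication pump |
| Devices named in one only | Cochlear implant | Pacemaker |
| Force | The sole absolute contraindication | TMS is not appropriate |

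Both device lists are examples, so the missing word alone would not matter. The proximity condition does: the examples in 4.4.6 illustrate hardware near the coil, and an open list of examples does not reach beyond the condition it illustrates.

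**One volunteer, step by step.** Take a person with AdSD, within the age range, with a stable, long-standing pacemaker, no severe or recent heart disease, no CNS-active medication and no other excluding feature. The pacemaker is assumed to be in the chest; the documents do not discuss its location.

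1. *Item (1).* Section 5.3 places the coil over the scalp. A chest device is not in close contact with it, so on the literal reading item (1) is not met.
2. *Item (2)a to f.* Pregnancy, bipolar disorder, epilepsy or recent seizure, brain lesion and medication that lowers seizure threshold do not concern devices. Heart disease under f depends on severity or recency, which this person lacks. It would catch some pacemaker carriers, but not necessarily all.
3. *The other eight AdSD exclusions.* These concern other dystonia, the larynx and voice, neurological disease, CNS medication, ability to do the tasks and capacity to consent. None addresses implanted devices.
4. *7.2.1.* The same person has a device that is named there as making TMS unsuitable.
5. *5.6.* The same person has an implanted device. That section says the criterion was set out earlier, but the earlier criterion is the narrower one in 4.4.6.

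The volunteer was chosen to show where the texts part. That nothing in 4.4.6 catches this person shows a gap in the wording and says nothing about how often it would arise.

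**Does anything close the gap?** The same item of 7.2.1 also restates the seizure-history and bipolar exclusions, and both match entries in 4.4.6. The device statement does not carry across in the same way. Section 4.4.4 asks about devices without stating a consequence. No text in the documents adds pacemakers to the list or removes the proximity condition.

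**The case against.** The strongest reply is that the protocol, read as a whole, already excludes this person.

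- *4.4.6 may not be exhaustive.* Its lists are labelled as primary exclusions, and restrictions appear elsewhere: item 3 of 7.2.1 says participants should not be taking blood thinners, which 4.4.6 also omits. The pacemaker statement in 7.2.1 can be read as a TMS contraindication in its own right. This stands in part. Against it, the asterisk sends the reader to the list in 4.4.6, and 4.4.7 speaks of listed criteria.
- *The proximity wording may not be meant strictly.* Item (1) names medication pumps without a location, so a looser reading is possible. This stands, and is a reason to grade the point low.
- *The intent is plain.* 4.4.4, 5.6 and 7.2.1 all point towards exclusion, and 4.4.7 lets the investigator remove a subject whose wellbeing would be compromised. This stands. It makes enrolment unlikely, and it also supports the edit, since the edit writes down what is already meant.
- *The working documents are not available.* The initial and on-site screening forms, the laboratory's TMS white paper, the FDA rTMS guidelines and Section 3 of the IRB protocol may already name pacemakers. If the form does, only a mismatch in wording remains.
- *An absolute contraindication and unsuitability are different things.* A device could make TMS inappropriate without being an absolute contraindication, so the two sentences are not strictly contradictory. This stands as logic. But 4.4.6 has a second tier for conditions that are not absolute yet still exclude, and it contains no device entry.

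A reader might infer that the protocol permits pacemaker carriers to enrol, or that some will be enrolled. The documents do not support that: 5.6 and 7.2.1 say the opposite. A reader might also count how many sections mention devices and how few state a distance limit. Such a count measures no effect, because 4.4.4 and 7.3 are not eligibility rules and would not be expected to state one.

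**Conclusion.** The point holds as a minor safety inconsistency. The written exclusion rule in 4.4.6 is narrower than the protocol's safety text in 7.2.1 and its disqualification text in 5.6, and for one narrow type of volunteer they give different answers.

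The conclusion rests on a literal reading of the proximity condition and on the pacemaker being in the chest. It concerns mainly the AdSD group (20 planned), because controls also face the general health-condition exclusion. The documents give no pacemaker frequency, so no enrolment probability is offered beyond saying that it should be low. Confidence is high that the texts differ. That confidence does not extend to any claim that a participant would be harmed. No endpoint, sample size or analysis is affected.

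**What to change.** In 4.4.6:

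1. Add to the TMS contraindications: *Cardiac pacemaker, medication pump, deep brain stimulator or other active implanted medical device, regardless of distance from the coil.*
2. In item (1), replace *The only absolute contraindication* with *An absolute contraindication*, so that the new line does not contradict it. Item (1) continues to cover other metallic hardware near the coil.
3. Confirm that the on-site TMS screening form carries the same item. If it already does, the form needs no change.

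The new line uses *active* deliberately. Section 5.6, read literally, covers any implanted device, including passive ones far from the coil. If that breadth is not intended, 5.6 should refer back to the revised list.

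The cost is one added line, a short wording change and a check of an existing form. The downside is that an occasional volunteer with an active implant remote from the coil is screened out, which 7.2.1 already intends.

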4.4.7 Exit/Discontinuation Criteria

Subjects will exit the study if any of the following conditions exist:

- 1. Subject voluntarily withdraws from the study.
- 2. Subject death.
- 3. Subject acquires any of the listed exclusion criteria.
- 4. Subject completes the protocol.
- 5. Subject's wellbeing, in the opinion of the Investigator would be compromised by study continuation.
- 6. Subject experiences an adverse event such as seizure.
- 7. DSMB and/or IRB recommendation

5.0 Study Procedures

5.1 Informed Consent

5.1.1 Informed Consent

All potential participants will receive a consent form describing this study and providing sufficient information for subjects to make an informed decision about their participation in the study. Please see consent form for specific wording that is tailored for each participant category: spasmodic dysphonia or healthy participant.

The consent form will be submitted with the protocol for review and will only be used once approval by the IRB for the study is given. The formal consent of a subject, using the IRB-approved consent form, will be obtained before that subject is submitted to any study procedure. This consent form will be signed by the subject and the investigator-designated research professional obtaining the consent. A copy of the IRB-approved consent form will be kept on-site and by the sponsor-investigator.

5.1.2 Vulnerable Populations

No vulnerable populations are included.

5.2 Allocation Scheme

Individuals will be assigned to each group based on their diagnosis and symptoms. All subjects will be assigned to the same procedures.

5.3 Clinical Procedures

Clinical assessment: Voice measures consisting of standard and published clinical scales will be collected for all participants to explore changes in voice quality (Zraick *et al.*, 2011; Samargia *et al.*, 2016). Voice quality will be measured by asking subjects to repeat 10 sentences with a high number of initial adductor phonemes, which often elicit symptoms in those with AdSD. These voice samples will be acquired digitally using a microphone. The frequency of voice breaks in the

recorded 10 sentences will be counted. These voice breaks will be the measure of disease severity. Other voice characteristics will be assessed using the Consensus Auditory-Perceptual Evaluation of Voice (CAPE-V) and the Voice Handicap Index (VHI). The CAPE-V is a reliable, valid clinical measure used by voice experts to assess voice quality. During a video recording, participants will be asked to repeat 6 sentences and then describe their voice problems. Voice experts will use the recording to rate voice quality based on several criteria (loudness, pitch, strain, breathiness, roughness, overall severity and others). In the current study, the total score in this scale will be used to rate the voice quality of participants before and after rTMS. The VHI is a self-administered questionnaire with questions about how often a given voice-related problem affects the life of participants. It reliably measures the influence of the subjects' voice disorder on their quality of life across three dimensions including: physical, functional and social. The total score for each participant will be measured before rTMS to assess how the voice disorder affects quality of life.

TMS testing: TMS testing will be performed to measure the corticospinal excitability before and after rTMS. TMS testing will be completed according to established methods (Kimberley and Di Fabio, 2010; Samargia *et al.*, 2014; Kimberley *et al.*, 2015a; Kimberley *et al.*, 2015b). Single and paired-pulse TMS testing will be delivered with a 70-mm figure-of-eight coil connected to a Magstim 200 stimulator (Magstim Company, Dyfed, UK), positioned on the scalp area over the left primary motor cortex. The laryngeal motor cortex will be identified by measuring the motor evoked potentials (MEP) of the thyroarytenoid muscle. Cortical stimulation will be spatially tracked with a neuronavigation system (BrainSight, Rogue Research Inc. Quebec, Canada) to decrease variability of stimulus delivery.

The TMS variables that will be measured in the study include single pulses that evoke a response in the muscle. The variable of interest is the amplitude of motor evoked potential (MEP) in response to different stimulation intensities and duration of silent period after the evoked response. Testing will include no more than 200 pulses (rTMS delivery will involve 1200 pulses — see below). Overall, the testing procedures will take approximately 60 minutes (30 minutes before and 30 after rTMS).

Fine-wire electrodes: All participants will undergo vocal muscle testing using fine-wire EMG. With the subject seated in a supportive chair, fine-wire EMG electrodes will be inserted in the thyroarytenoid muscles (the "vocal cords") by a trained physician, [name]. The skin on the throat will be numbed using a lidocaine cream and also an injection of a lidocaine (numbing) agent. Once the skin has been numbed, the electrode will be placed into the muscle. To place the electrode, two fine wires will be inserted using a small gauge needle (30MM, 27 guage) with the edges of the wire electrode hooked around the tip of the needle and connected to an EMG machine. The needle will be passed through the skin and into the larynx. When the vocal cord is entered, an increased EMG signal associated with speech is detected. The needle will then be removed, leaving only the flexible wires in place.

Once the needle is removed, participants will not feel the presence of the electrode. Participants will be able to breath, talk and move their head with the electrode in place. At the end of the testing for vocal muscles, the electrodes will be gently pulled out. This process is nearly unnoticeable due to the very small diameter of the wires. Procedures will be the same as previous study (IRB # 0608M91226. Study Title "Pathophysiology of Spasmodic dysphonia: a TMS study").

rTMS application: rTMS will be delivered to the left laryngeal motor cortex with a hand-held figure-of-eight coil positioned over the scalp and connected to a Rapid² magnetic stimulator (Magstim Company, Dyfed, UK). The protocol described below is FDA approved and has been used extensively by our lab without incident. The risk of seizure is minimized by using a low rate of stimulation and a sub-threshold level of intensity.

All participants will receive low-frequency rTMS pulses. rTMS at a low frequency is known to be inhibitory to the neurons receiving the stimulation. rTMS will be delivered at 90% of the threshold which elicits MEPs in the thyroarytenoid muscle, as determined during TMS testing. Pulses will be delivered at a frequency of 1 Hz without interruption (total = 1200 pulses) which has been shown to alter cortical excitability and behavior (Gerschlager *et al.*, 2001). rTMS delivery will take 20-30 minutes. During the stimulation, the subject will only feel a slight tapping sensation on the head due to the repetitive discharging of the cutaneous nerves in the scalp. After stimulation, corticospinal excitability and voice quality will be measured.

Because the purpose of this study is to collect preliminary data for feasibility and safety, sham rTMS will not be tested.

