3.0 Study Objectives

3.1 Primary Objective

The purpose of this project is to determine safety, feasibility and response to 1Hz rTMS to the laryngeal motor cortex in individuals with AdSD and healthy people. The following Aims will be tested:

Aim 1: Determine safety and feasibility for the application of 1 Hz rTMS to the laryngeal motor cortex.

Hypothesis: rTMS to laryngeal motor cortex will be safe and feasible as measured by no serious adverse events and 100% study completion by participants.

Aim 2: Determine amount of intracortical inhibition in the laryngeal motor cortex as measured in the thyroarytenoid both within and between groups before and after rTMS. Hypotheses:

- The AdSD group will demonstrate less inhibition in the laryngeal motor cortex at baseline.
- rTMS will increase intracortical inhibition for the laryngeal motor cortex in both groups, but AdSD individuals will show greater changes.
- There will be no difference between groups at posttest suggesting a normalizing of intracortical inhibition.

Aim 3: Explore changes in voice quality following rTMS with a blinded assessment by a voice expert.

Hypothesis: Clinical scores will show a trend toward improved voice quality in people with AdSD.

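### The blinded CAPE-V rating uses a video that includes the participant's own account of their voice, and nothing hides whether it was recorded before or after rTMS

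*Combined protocol and SAP*

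**What the plan says.** Section 3.1 sets Aim 3 as follows: "Explore changes in voice quality following rTMS with a blinded assessment by a voice expert". Its hypothesis is directional and confined to one group: "Clinical scores will show a trend toward improved voice quality in people with AdSD". Section 4.3.2 repeats the commitment for the secondary endpoints: "clinical voice measures collected before and after rTMS procedures with a blinded assessment by a voice expert". Neither section says whether the expert is blind to group, time point or both, or how the blind is kept.

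Section 5.3 (Clinical assessment) describes what is rated: "During a video recording, participants will be asked to repeat 6 sentences and then describe their voice problems". It continues: "Voice experts will use the recording to rate voice quality based on several criteria". On timing it says that "the total score in this scale will be used to rate the voice quality of participants before and after rTMS". Under rTMS application, the same section states that "sham rTMS will not be tested".

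The protocol text mentions no trimming of the recording, audio-only extract, coded file names, random playback order, or instruction to participants about what to leave unsaid. Sections 5.5, 6.1 and 6.2 add no safeguard.

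**The concern.** A blind on a before/after rating protects the result only if the rater cannot tell which recording is which. Here the rated file ends with free speech about the very thing being rated. The speaker may have just had stimulation that they know to be active, and a remark that the voice feels different, or a mention of the session, would identify the recording as the later one.

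All participants receive active rTMS, so knowing that a recording is the later one is the same as knowing it is treated. CAPE-V is a perceptual judgement and the protocol predicts improvement, so a rater's expectation could enter the before/after change. Section 4.4.1 intends the pilot data to supply effect sizes for later studies, and a biased change would pass into their planning.

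**Working it through.** The protocol gives no figure to reproduce for this point, and no error rate is involved because the analysis in 6.2 is descriptive. The check is a side-by-side reading, followed by simple bookkeeping.

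**Step 1: promise against procedure.** Sections 3.1 and 4.3.2 promise a blinded rating. Section 5.3 supplies a video with a self-description and has the experts work from it. Nothing between the camera and the rater is described. Followed as written, the file can carry the time point.

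**Step 2: the spoken cue.** The prompt is about voice problems, not about change or stimulation. A participant may still comment on change after rTMS. This is plausible, but the text does not show that it will happen.

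**Step 3: the visual cue.** Four statements bear on it:
- 5.3 sets the rTMS intensity from a threshold measured in the thyroarytenoid muscle, so the fine wires must be in place before rTMS.
- 5.3 takes the wires out when vocal-muscle testing ends.
- The 5.5 table lists the baseline voice assessment before the TMS pre-tests.
- The 5.5 table lists the later voice assessment after rTMS but before the TMS post-tests.

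Taken together, the wires are probably in place for the later video and possibly absent from the baseline one. This remains an inference. The time of insertion is not stated, and one sentence in 5.3 names the excitability measurement ahead of voice quality after stimulation.

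**Step 4: how many recordings matter.** Section 4.4.1 plans 20 AdSD participants and 20 controls. With two CAPE-V recordings each, there are 40 × 2 = 80 recordings in all. The Aim 3 hypothesis uses only the AdSD group: 20 × 2 = 40.

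**Step 5: form of the bias.** Let Δ be the true mean AdSD change, and d the average amount by which expectation moves the later AdSD ratings. The expected observed change is Δ + d. The sample size does not appear in the bias term, so more participants would not reduce it.

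Controls are also rated twice. If Δ_C is their true change and their later ratings move by d_C, the between-group difference in change is (Δ − Δ_C) + (d − d_C). The bias cancels only if d = d_C. That cannot be assumed, because the predicted improvement concerns AdSD alone and near-normal voices leave little room to be scored better. The documents give no value or range for d or d_C.

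**Step 6: what is outside the point.**
- Voice breaks are counted from a separate microphone recording of 10 sentences with no self-description, although 5.3 does not say who counts them or whether the order is masked.
- The VHI is taken before rTMS only.
- The primary endpoint in 4.3.1 is a TMS measure.

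**The case against.** The strongest reply is that silence is not failure. The protocol commits twice to a blinded assessment, and rating from recordings instead of live is what makes coding and shuffling possible. Section 14.0 lists an experiment checklist and a CAPE-V form that are not among the documents and might hold handling rules. It is also not explicit that the self-description is repeated after rTMS: the 5.5 table lists a fuller clinical assessment before stimulation and only a voice quality assessment after it. These points stand as limits. A reader might infer that the blind is broken, and the text does not support that. It shows only that the blind is unprotected.

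A second reply concerns group. A reader might object that a control will say there is no voice problem and so reveal their group. This matters little. The hypothesis is a change within AdSD, and the disorder may be audible in the six sentences anyway, so audio-only rating would not secure group masking either.

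A third reply is that the controls act as a check, since they too are rated before and after. This stands in part: a shift common to both groups would show in the controls. It would not remove a shift that is larger in AdSD.

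A fourth reply is that the self-description belongs to the CAPE-V recording as 5.3 describes it, so dropping it alters the material behind an established scale. This is a real cost, but a small one. A neutral-topic speech sample would keep some free speech.

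What remains is that the procedure as written puts a time-point cue in front of the rater and describes nothing that removes it.

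**Conclusion.** The concern holds in a limited form. The CAPE-V blind to time point is not secured by the procedure in 5.3. With no sham, rater expectation could bias the within-AdSD before/after CAPE-V change, on up to 40 recordings from 20 participants, and any effect size taken from it. The bias equals d, whose size is unknown.

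The conclusion assumes that the self-description is recorded at both time points, that raters receive the recording unedited, and that no unseen attachment sets masking rules. The wire cue is an additional possibility and the conclusion does not depend on it.

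A reader might also infer that all 80 recordings, or the whole of Aim 3, are compromised. The documents do not support that. The control recordings do not enter the hypothesis, and the voice-break count, which 5.3 treats as its severity measure, lacks the self-description. Aim 3 is exploratory and no test is affected. This is a worthwhile, inexpensive improvement and does not threaten the study's primary result.

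**What to change.** In 5.3, state that CAPE-V raters are masked to time point and say how:
- Rating takes place after collection, from files that carry random codes.
- Files are presented in one shuffled order across participants and time points.
- The rated file is the audio of the 6 sentences, with the self-description removed or replaced by a speech sample on a neutral topic.
- The same coding and shuffling apply to the voice-break count.

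Coding and shuffling alone would not be enough if the video and the self-description stayed in the file, because the cue lies in the content.

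The cost is protocol wording plus exporting, trimming and renaming files. It needs no new visits or staff, but must be in place before rating begins. The downside is that raters lose the picture and the free-speech account of the voice problem, a small departure from the recording that 5.3 describes.
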